### XIII. CRITERIA FOR RESPONSE FOR ACUTE LEUKEMIAS AND MDS

International Working Group Criteria will be used to define response.

1. Complete remission (CR): The patient must be free of all symptoms related to leukemia and have an absolute neutrophil count  $\geq 1.0 \times 10^9/L$ , platelet count  $\geq 100 \times 10^9/L$ , and normal bone marrow differential ( $\leq 5\%$  blasts).
2. Complete remission without platelet recovery (CRp): As per CR but platelet count  $< 100 \times 10^9/L$ .
3. Partial remission (PR): CR with 6 to 25% abnormal cells in the marrow or 50% decrease in bone marrow blasts.
4. Marrow CR: Bone marrow:  $\leq 5\%$  myeloblasts and decrease by  $\geq 50\%$  over pre-treatment (MDS only)
5. Morphologic leukemia-free state: Normal marrow differential ( $< 5\%$  blasts); neutrophil and platelet counts are not considered. (AML only)
6. Hematologic Improvement (HI): HI should be described by the number of individual, positively affected cell lines (e.g. HI-E; HI-E + HI-N; HI-E + HI-P + HI-N)
  - a) Erythroid response (HI-E):
    - Major response: For patients with pretreatment hemoglobin less than 11 g/dL, greater than 2 g/dL increase in hemoglobin; for RBC transfusion-dependent subjects, transfusion independence.
    - Minor response: For patients with pretreatment hemoglobin less than 11 g/dL, 1 to 2 g/dL increase in hemoglobin; for RBC transfusion-dependent patients, 50% decrease in transfusion requirements.
  - b) Platelet response (HI-P):
    - Major response: For patients with a pretreatment platelet count less than  $100 \times 10^9/L$ , an absolute increase of  $30 \times 10^9/L$  or more; for platelet transfusion-dependent patients, stabilization of platelet transfusion independence.
    - Minor response: For patients with a pretreatment platelet count less than  $100 \times 10^9/L$ , a 50% or more increase in platelet count with a net increase greater than  $10 \times 10^9/L$  but less than  $30 \times 10^9/L$ .
  - c) Neutrophil response (HI-N):
    - Major response: For absolute neutrophil count (ANC) less than  $1.5 \times 10^9/L$  before therapy, at least a 100% increase, or an absolute increase of more than  $0.5 \times 10^9/L$ , whichever is greater.
    - Minor response: For ANC less than  $1.5 \times 10^9/L$  before therapy, ANC increase of at least 100%, but absolute increase less than  $0.5 \times 10^9/L$ .

7. Progression/relapse after HI: One or more of the following: a 50% or greater decrement from maximum response levels in granulocytes or platelets, a reduction in hemoglobin concentration by at least 2 g/dL, or transfusion.

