**V. PATIENT ELIGIBILITY:**

**INCLUSION:**

1. All patients with histologically or cytologically confirmed relapsed or refractory AML [except acute promyelocytic leukemia], or HRMDS (Int-2 high risk by IPSS or >10% blasts in marrow).
2. Patients must be 18 years or older.
3. Patients must have a performance status of 0-2 (Zubrod scale).
4. Patients must have adequate renal function (serum creatinine ≤ 1.3 mg/dL and/or creatinine clearance > 40 mL/min). Patients with renal dysfunction due to organ infiltration by disease may be eligible after discussion with the P.I., (up to creatinine ≤ 2.0) and appropriate dose adjustments will be considered.
5. Patients must have adequate hepatic function (bilirubin ≤ 2.0 mg/dl; SGOT or SGPT ≤ 3X the ULN for the reference lab unless due to leukemia or congenital hemolytic disorder or bilirubin). Patients with hepatic dysfunction (SGOT/SGPT up to ≤ 5X ULN) due to organ infiltration by disease may be eligible after discussion with the P.I., and appropriate dose adjustments will be considered.
6. Patients must have normal cardiac ejection fraction.
7. QTc interval ≤ 480 msec.

8. Patients must sign an informed consent form indicating that they are aware of the investigational nature of this study, in keeping with the policies of the hospital.
9. Female patients must not be pregnant or lactating. Female patients of childbearing potential (including those <1 year post-menopausal) and male patients must agree to use contraception.

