## **XX. STATISTICAL CONSIDERATIONS**

The objective of this study is to assess the efficacy and safety of treatment of E7070 with chemotherapy in Leukemia patients. The efficacy will be measured by the overall response (CR + CRp + PR+ marrow clearance of blast) during Cycle 1. The sample size and stopping rules will be determined according to Simon's two-stage design.

The efficacy will be assessed based on the Simon's two-stage Minmax design. The new treatment will be considered promising if the response rate is 25% or higher, and will be considered unworthy of further investigation if response rate is 10% or less. The maximum sample size of 40 patients is chosen to differentiate between response rates of 10% and 25% with 90% power at a significance level of 0.1. In particular, 27 patients will be enrolled at the first stage. If there are two or fewer patients with response, the trial will be terminated; otherwise another 13 patients will be treated for a total of 40 patients. If, among 40 patients, there are 6 or fewer patients with response, the treatment will be concluded ineffective. The probability of early termination due to futility is 0.48.

A Bayesian sequential monitoring method will be used to monitor the toxicity. We stop the trial if the toxicity is likely to be greater than 33%. That is, stop the trial if

$$\text{Prob \{toxicity rate > 33\% | data\}} > 0.80.$$

The prior distribution of toxicity rate is assumed to be beta (0.67, 1.33). Following this rule, the trial will be terminated due to toxicity if  $[\# \text{ toxicity}]/[\# \text{ patients evaluated}] \geq 2/3, 3/5, 4/7, 5/10, 6/13, 7/15, 8/18, 9/20, 10/23, 11/26, 12/28, 13/31, 14/34, 15/37, \text{ or } 16/40$ .

A toxic event will be defined as death or a CTCAE 4.0 grade 3/4 non-hematological toxicity related to study drug lasting or 7 days or more.

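### The partial-remission definition sets a marrow level without requiring a fall from baseline, so an unchanged marrow can count as a response in the Simon decision

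*Combined protocol and SAP*

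**What the plan says.** Section XIII states that "International Working Group Criteria" define response, then lists the categories. Item 3 gives PR as "CR with 6 to 25% abnormal cells in the marrow or 50% decrease in bone marrow blasts". Item 1 supplies the CR conditions that the first alternative carries over. It begins "The patient must be free of all symptoms related to leukemia and have an absolute neutrophil count" of at least 1.0 × 10⁹/L, and it also needs platelets of at least 100 × 10⁹/L. Item 4, Marrow CR (MDS only), joins a level and a fall: at most 5% "myeloblasts and decrease by" at least 50% over pre-treatment.

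Section V, inclusion 1, admits relapsed or refractory AML with no stated blast minimum, and high-risk MDS by IPSS category "or >10% blasts in marrow". Neither the inclusion nor the exclusion list bars patients whose neutrophils and platelets are already at CR level.

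Section XX puts PR into the decision: "The efficacy will be measured by the overall response (CR + CRp + PR+ marrow clearance of blast) during Cycle 1". The trial stops with 2 or fewer responses in 27 and concludes ineffective with 6 or fewer in 40. The descriptive analysis also includes PR in the overall response rate and its 95% confidence interval. Section IV.A and footnote 10 of the Schedule of Assessments use PR to identify who may receive additional cycles.

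**The concern.** The 6 to 25% range is an end state. It shows a response only if the patient started outside it, and the eligibility criteria do not ensure that. A patient who enters with marrow already in that range and does not change can be scored a PR.

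The second alternative raises a different question. It measures change, but the sentence does not say whether the CR conditions govern it. If they do not, a fall from 80% to 40% blasts without count recovery is a PR. If they do, it is a PR only with recovered counts. Two assessors could classify the same patient differently.

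The go/no-go decision is at stake. Patients counted without any marrow improvement make an inactive regimen more likely to be called promising and the futility stop less likely to act. With thresholds of 3 in 27 and 7 in 40, one or two classifications can settle the result.

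**Working it through.** **Step 1. Does the wording allow an unchanged marrow to count?** Take a high-risk MDS patient with 15% marrow blasts before treatment and 15% afterwards, no leukemia symptoms, neutrophils of at least 1.0 and platelets of at least 100 × 10⁹/L.

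- Eligibility (Section V): 15% exceeds 10%, and no criterion excludes on adequate counts. Eligible.
- PR, first alternative (Section XIII item 3): CR conditions other than the marrow are met, and 15% lies between 6 and 25%. PR, with a marrow change of 0%.
- Section XX: PR is counted.

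This result does not depend on how the second alternative is read. No other section adds a requirement for a fall to the 6 to 25% alternative.

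**Step 2. Reproduce the design.** Inputs from Section XX: n₁ = 27, r₁ = 2, n = 40, r = 6, p₀ = 0.10, p₁ = 0.25. For a counted response rate p, with X₁ ~ Bin(27, p) and X₂ ~ Bin(13, p):

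- early termination: PET(p) = P(X₁ ≤ 2)
- promising: P(p) = Σ over x ≥ 3 of P(X₁ = x) · P(X₂ ≥ 7 − x)

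At p = 0.10, PET = 0.0581 + 0.1744 + 0.2520 = 0.4846 after rounding the sum, against 0.48 in the plan. P(0.10) = 0.0977, against a level of 0.1. At p = 0.25, P = 0.9001, against 90% power. A search over two-stage designs returns the same 27/2, 40/6 as minimax. The sample-size arithmetic is correct.

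**Step 3. What added PRs would do.** Suppose the rate is 10% when a PR needs a real fall, and a further δ of all patients count only because no fall is required. The counted rate is p = 0.10 + δ. The documents give no value for δ, so it is an assumption shown as a range.

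| δ (assumed) | counted rate | expected extra in 40 (40δ) | P(promising) | PET |
|---|---|---|---|---|
| 0 | 0.10 | 0 | 0.098 | 0.485 |
| 0.01 | 0.11 | 0.4 | 0.142 | 0.417 |
| 0.02 | 0.12 | 0.8 | 0.195 | 0.355 |
| 0.05 | 0.15 | 2 | 0.388 | 0.207 |

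One added point, less than half a patient in 40 on average, already takes the false-positive rate above the planned 0.1.

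**Step 4. What a repair must avoid.** If PR needed both a fall of at least 50% and a residual of at least 6%, the baseline would have to be at least 6 / 0.5 = 12%. A patient entering at 11% who halves reaches 5.5%, below the range. Simply joining the two alternatives would therefore make PR unattainable for some eligible high-risk MDS patients.

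**The case against.** Four arguments count against the point.

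- **The *or* may be intended.** A reader might infer that it is a slip for *and*. The documents do not show that. Section XIII covers AML and MDS, refers to outside criteria whose text is not reproduced, and labels some items for one disease only, so the two alternatives may be disease-specific. Marrow CR is a different category, and item 5 (leukemia-free state) sets a level with no fall. This stands: the wrong conjunction is not proven. The literal result in Step 1 does not need it.
- **The case is narrow.** The patient must start at 6 to 25%, be symptom-free and have counts at CR level in Cycle 1. Idarubicin is given on days 9 to 11, and the drug section puts count recovery at 21 to 28 days. Counted from day 11, that is about days 32 to 39, whereas disease assessment is at day 28 ± 3, although it may be delayed or repeated. The stated focus is also relapsed or refractory AML. This stands and makes a small δ more plausible than a large one.
- **Halving of blasts is real change.** A reader might treat every PR under the second alternative as spurious and cite a 10-point inflation, at which P(promising) would be 0.71. The documents support neither. Whether a 50% fall without a ceiling should count is a choice of endpoint, and 10 points would be 4 patients in 40 with no source.
- **The reference rates may already fit the broad definition.** Section XX gives no source for 10% or 25%, and the Background quotes less than 10% to 20%. If both rates were set for PR as written, the false-positive rate against that null is as planned. The counted responses would still include patients without marrow improvement.

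**Conclusion.** The point holds as a gap and an ambiguity in the endpoint definition. Followed as written, item 3 can score a marrow with no change as a response, and that response enters both the Simon count and the response-rate estimate. Whether the CR count conditions apply to the 50% alternative is not stated.

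The size cannot be fixed from the documents. Under the assumed additions of 1, 2 or 5 points to a true rate of 10%, P(promising) is 0.14, 0.19 or 0.39 instead of 0.098, and early termination is 0.42, 0.36 or 0.21 instead of 0.48. These figures illustrate how sensitive the rule is and do not estimate what would occur. They assume that 10% refers to responses with real improvement. Cases under the first alternative are probably few. The design figures themselves are sound. Severity: should fix.

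**What to change.** For the Simon count and the response-rate estimate:

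1. Count a PR only if marrow blasts have fallen by at least 50% from the pre-treatment marrow.
2. State whether the CR blood-count conditions apply to that requirement.
3. If a residual limit is kept, write it as a ceiling of 25% and not as a 6 to 25% window, so that high-risk MDS patients with baseline blasts below 12% can still qualify.

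The cost is a short edit to Section XIII and a cross-reference in Section XX. The sample size and thresholds stay as they are. A pre-treatment marrow is already required. Section VII lets it be waived if done within 3 months, so the text should say which marrow is the baseline.

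The downside is a somewhat lower observed response rate. If the 25% target assumed the broader definition, power falls too: if tightening took the counted rate from 25% to 20% (assumed), P(promising) would be 0.71 instead of 0.90. The team should state which definition the 10% and 25% refer to.

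Section IV.A and footnote 10 of the Schedule of Assessments use PR to decide on additional cycles. They should be reconciled with the revised definition. No treatment rule is proposed here.

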#### **XIV. CRITERIA FOR REMOVAL FROM THE STUDY**

The investigator may remove patients from the study for any of the following reasons:

- Clinically significant progressive disease
- Failure to achieve any clinically significant response after two cycles of therapy
- Unacceptable adverse events/toxicities
- Investigator thinks a change of therapy would be in the best interest of the patient (e.g. potential for worsening of existing infection or other toxicities)
- The patient has an intercurrent, non-leukemia-related illness that would, in the judgment of the investigator, affect assessments of clinical status to a significant degree and require discontinuation of protocol therapy
- Patient request
- Patient is non-compliant with protocol requirements

#### **XV. ADVERSE EVENTS, SERIOUS ADVERSE EVENTS AND REPORTING**

**A. Adverse Event (AE):** Any untoward medical occurrence in a subject or clinical investigation subject administered an investigational product. An AE does not necessarily have a causal relationship with the medicinal product. For this study, the medicinal product is E7070.

The criteria for identifying AEs are:

- Any unfavorable and unintended sign (including an abnormal laboratory finding), symptom, or disease temporally associated with the use of a medicinal product, whether or not considered related to the medicinal product
- Any new disease or exacerbation of an existing disease
- Any deterioration in non-protocol-required measurements of laboratory value or other clinical test (e.g., ECG or X-ray) that results in symptoms, a change in treatment, or discontinuation from study drug
- Recurrence of an intermittent medical condition (e.g. headache) not present at Baseline.

An abnormal laboratory test result may be considered as an adverse event if the identified laboratory abnormality leads to any type of intervention whether prescribed in the protocol or not.

A laboratory result should be considered by the Investigator to be an adverse event if it:

- results in the withdrawal of study treatment
- results in withholding of study treatment pending some investigational outcome
- medical evaluation, results in the initiation of an intervention (e.g. potassium supplement for hypokalemia)
- Any out of range laboratory value that in the Investigator's judgment, fulfills the definitions of an AE with regards to subject's medical profile
- Increases in severity compared to Baseline by  $\geq 2$  NCI grades (see Appendix A for NCI CTCAE Ver 4.0 criteria), with the exception of lymphocytes, albumin, cholesterol, glucose and phosphate. For these tests, a change of  $\geq 2$  grades will be evaluated by the Investigator to determine if they are of clinical significance and if so, will be considered an adverse event.

Abnormal laboratory values should not be listed as separate AEs if they are considered to be part of the clinical syndrome that is being reported as an AE. Any laboratory abnormality considered to constitute an adverse event should be reported on the Adverse Event Case Report Form (CRF).

It is the responsibility of the Investigator to review all laboratory findings in all subjects and determine if they constitute an adverse event. Medical and scientific judgment should be exercised in deciding whether an isolated laboratory abnormality should be classified as an adverse event.

## **B. Reporting of Adverse Events**

Adverse events will be recorded by the research personnel on a MDACC Adverse Event log. The Investigator or physician designee is responsible for verifying and providing source documentation for all adverse events and assigning the attribution for each event for all subjects enrolled on the trial. Adverse event logs will be scanned into Clinic Station when a patient is removed from study or approximately every 6 months.

For this protocol, adverse events and protocol specific data will be entered into PDMS/CORe. PDMS/CORe will be used as the electronic case report form for this protocol.

All AEs encountered during the clinical study will be reported on the CRF. All AEs, regardless of relationship to study drug or procedure, should be collected beginning from the time the subject signs the study consent. Adverse events in clinical investigation subjects include any change in the subject's condition. This includes symptoms, physical findings, or clinical syndromes.

Subjects with AEs that are ongoing at the subject's last study visit must be followed until resolution or for 30 days after the subject's last study visit, whichever comes

first. Adverse events that are reported during the Follow-up Period will be recorded on the Adverse Events CRF and followed until resolution or for up to the 30 days after the subject's last study visit, whichever comes first, with the exception that SAEs will be followed until the event resolves or the event or sequelae stabilize.

**Every effort must be made by the Investigator to categorize each AE according to its severity and its relationship to the study treatment.**

### **C. Assessing Severity of Adverse Events**

The National Cancer Institute (NCI) Common Terminology Criteria for Adverse Events (CTCAE Ver 4.0) is used to assign severity scales to AEs (Appendix A). They are:

Grade 1 = Mild

Grade 2 = Moderate

Grade 3 = Severe

Grade 4 = Life Threatening

Grade 5 = Death

AEs that are not defined in the NCI CTCAE should be evaluated for severity according to the following scale:

Grade 1 = Mild

Grade 2 = Moderate

Grade 3 = Severe

In addition, all AEs reported using the NCI CTCAE classification and graded as 4 or 5 are to be considered serious.

The criteria for assessing severity are different than those used for seriousness.

### **D. Assessing Relationship to Study Treatment**

Items to be considered when assessing the relationship of an AE to the study treatment are:

- Temporal relationship of the onset of the event to the initiation of the study treatment
- The course of the event, considering especially the effect of discontinuation of study treatment or reintroduction of study treatment, as applicable
- Whether the event is known to be associated with the study treatment, or with other similar treatments
- The presence of risk factors in the study subject known to increase the occurrence of the event

- The presence of non-study treatment related factors which are known to be associated with the occurrence of the event

## **E. Classification of Causality**

**Not Related:** A causal relationship between the study treatment and the AE is not a reasonable possibility.

**Related:** A causal relationship between the study treatment and the AE is a reasonable possibility. The Investigator must further qualify the degree of certainty as “**possible**” or “**probable**.”

## **F. REPORTING REQUIREMENTS**

Reporting requirements will be as per institutional guidelines.

### **Adverse events (AE) related to study conditions**

The serious adverse event (SAE) reporting period will begin with the signing of the informed consent.

AEs should be followed to resolution or stabilization, and reported as SAEs if they become serious. This also applies to patients experiencing AEs that cause interruption or discontinuation of investigational product, or those experiencing AEs that are present at the end of their participation in the study. Such patients should receive post-treatment follow-up as appropriate.

### **Serious Adverse Event Reporting (SAE)**

An adverse event or suspected adverse reaction is considered “serious” if, in the view of either the investigator or the sponsor, it results in any of the following outcomes:

- Death
- A life-threatening adverse drug experience – any adverse experience that places the patient, in the view of the initial reporter, at immediate risk of death from the adverse experience as it occurred. It does not include an adverse experience that, had it occurred in a more severe form, might have caused death.
- Inpatient hospitalization or prolongation of existing hospitalization
- A persistent or significant incapacity or substantial disruption of the ability to conduct normal life functions.
- A congenital anomaly/birth defect.

Important medical events that may not result in death, be life-threatening, or require hospitalization may be considered a serious adverse drug experience when, based upon appropriate medical judgment, they may jeopardize the patient or subject and may require medical or surgical intervention to prevent one of the outcomes listed in this definition. Examples of such medical events include allergic bronchospasm requiring intensive treatment in an emergency room or at home, blood dyscrasias or convulsions that do not result in inpatient hospitalization, or the development of drug dependency or drug abuse (21 CFR 312.32).

- Important medical events as defined above, may also be considered serious adverse events. Any important medical event can and should be reported as an SAE if deemed appropriate by the Principal Investigator or the IND Sponsor, IND Office.
- All events occurring during the conduct of a protocol and meeting the definition of a SAE must be reported to the IRB in accordance with the timeframes and procedures outlined in “The University of Texas M. D. Anderson Cancer Center Institutional Review Board Policy for Investigators on Reporting Unanticipated Adverse Events for Drugs and Devices”. Unless stated otherwise in the protocol, all SAEs, expected or unexpected, must be reported to the IND Office, regardless of attribution (within 5 working days of knowledge of the event).
- **All life-threatening or fatal events**, that are unexpected, and related to the study drug, must have a written report submitted within **24 hours** (next working day) of knowledge of the event to the Safety Project Manager in the IND Office.
- Unless otherwise noted, the electronic SAE application (eSAE) will be utilized for safety reporting to the IND Office and MDACC IRB.
- Serious adverse events will be captured from the time of the first protocol-specific intervention, until 30 days after the last dose of drug, unless the participant withdraws consent. Serious adverse events must be followed until clinical recovery is complete and laboratory tests have returned to baseline, progression of the event has stabilized, or there has been acceptable resolution of the event.
- Additionally, any serious adverse events that occur after the 30 day time period that are related to the study treatment must be reported to the IND Office. This may include the development of a secondary malignancy.

